3.4.3.4 Phase 3 Exploratory Efficacy Endpoints

In an exploratory analysis, descriptive statistics for least-square mean difference of change from baseline in QOL-B respiratory domain score and MACrO₂ total scaled score, and by-patient sputum culture conversion by Month 6 will be presented by age category, ALIS use at baseline, presence-absence of any fibrocavitary disease, chest cavity category (non-cavitary, cavity diameter ≤ 3 cm, cavity diameter > 3 cm from EDC), MAC resistance phenotype (ie, macrolide-resistant, amikacin IV-resistant, and amikacin (liposomal, inhaled)-resistant), sex, baseline creatinine clearance category (<60 mL/min, ≥60 mL/min to <90 mL/min, or ≥ 90 mL/min), BMI category (<18.5 vs ≥18.5 kg/m²), and country of enrollment in the Micro-ITT Population. Forest plots of the estimated treatment difference and 95% confidence interval will be presented across all subsets, but no formal statistical testing will be performed.

Change from baseline in continuous PROs, including QOL-B respiratory domain score, MACrO₂ total scaled score, NTM Symptoms Module Domain score, and SGRQ-C total score, will be analyzed using a mixed model for repeated measures (MMRM) that includes randomized treatment, visit (from Baseline to Month 6 inclusive), and treatment by visit interaction as explanatory variables, and corresponding baseline score as a continuous covariate. Treatment visit and treatment by visit interaction will be fixed effects in the model, and treatment by visit interaction will remain in the model regardless of significance. The participant effect will be fitted as a random effect and an unstructured covariance structure will be assumed for within participant variation. If this model does not converge then the covariance matrices of Toeplitz, first-order autoregressive, and compound symmetry will be used in that order until the model converges. The analysis will be performed using PROC MIXED in SAS and the resulting F-tests will be based on Kenward-Roger's adjusted degrees of freedom. Least squares means, 95% confidence intervals, and p-values of the treatment comparisons at Month 3 and Month 6 will be presented for both Micro-ITT and PP populations, along with an assessment of the difference between slopes from baseline to Month 6 and residual plots will be provided to examine departures from normality and/or outliers.

By-patient sputum culture conversion by Month 6 and by-patient microbiological improvement at Month 3 and Month 6 by epetaborole MIC across all baseline pathogens and within each individual baseline pathogen species will be summarized by treatment group in the Micro-ITT Population. By-pathogen microbiological sputum culture conversion at Month 6 and by-pathogen microbiological improvement at Month 3 and Month 6 will be summarized by treatment group for each individual baseline pathogen in the Micro-ITT Population.

Time (in days) to first sustained improvement in QOL-B respiratory domain score by a threshold (11.1 points) determined as part of a blinded anchor-based psychometric analysis of pooled Phase 2 data, time (in days) to first sustained MACrO₂ PRO-based clinical response through Month 6, and time to first sustained improvement in MACrO₂ total scaled score by a threshold (11.3 points) determined as part of a blinded anchor-based psychometric analysis of pooled Phase 2 data will be summarized by treatment group in the Micro-ITT Population. The first sustained PRO-based clinical response through Month 6 is defined as the earliest study day at which the weekly (or monthly) PRO assessment meets the criteria of clinical response and which is maintained consistently at all available subsequent assessments through Month 6 (inclusive). Missing assessments will be excluded from sustained response determination. A Kaplan-Meier analysis and corresponding plot will be provided by treatment, and estimated event rates by treatment arm based on the plot will be provided for study days 29, 57, 85, 113, 141, and 169 to align with protocol specified visit months. Patients who fail to achieve sustained response by Month 6 or discontinue early from the study will be censored at their last day of treatment or the day of their Month 6 visit, whichever is earlier. In an alternative approach to assess the impact of censoring on the analysis results, the same analysis will be performed where all patients who fail to achieve sustained response and who discontinue from the study prior to Month 6 will be censored at the maximum allowable duration of 6 Months. Time to event will also be analyzed using a Cox proportional hazard model with the same variables as the previous exploratory analysis, and hazard ratio and 95% confidence intervals at Month 6 will be reported.

Radiographic response at Month 6 and at EOT, defined as overall change from baseline based on blinded central reading of chest CT will be summarized at baseline and at Month 6 and at EOT and the proportion of patients meeting the criteria of overall improvement from baseline (Y/N; with Yes defined as those categorized as either "Resolution" or "Improvement", and No as all other categories or missing interpretation) will be presented by treatment group, along with the treatment difference and associated 95% confidence interval, calculated using the method of Miettinen and Nurminen, including stratification by baseline ALIS use and presence or absence of any fibrocavitary disease in the Micro-ITT Population.

Rate of decreased susceptibility among postbaseline MAC isolates, defined as a ≥ 4 -fold increase in epetraborole MIC relative to the baseline isolate MIC at any post-baseline follow-up visit, among patients remaining MAC culture-positive at Month 4 or later will be summarized by treatment group in the Micro-ITT Population. Rates of decreased clarithromycin or IV amikacin susceptibility, defined as a change from interpretation of Susceptible or Intermediate at baseline to Resistant at any post-baseline follow-up visit according to the interpretive criteria provided in Table 1, will be summarized similarly.

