2.2 Study Design

2.2.1 Overview

Refer to Protocol Section 3.1 Summary of Study Design for full details of the study overview.

Briefly, this is a pivotal Phase 2/3, double-blind, placebo-controlled study of eptraborole + OBR versus placebo + OBR in patients with treatment-refractory MAC lung disease. This study will enroll adult patients with treatment-refractory MAC lung disease who meet all eligibility criteria.

This study features a sequential Phase 2/3 approach with an initial Phase 2 assessment of clinical responses (based on clinical symptoms and/or functional assessments), microbiological responses, safety, and PK associated with oral eptraborole, prior to the superiority analysis of oral eptraborole versus placebo in the Phase 3 part of the study.

In both the Phase 2 and Phase 3 parts of the study, each patient will complete multiple PRO measures including MACrO₂, QOL-B, NTM Symptoms Module, SGRQ-C, and global patient and clinician assessment scales (Patient Global Impression of Severity [PGIS], Patient Global Impression of Change [PGIC], Clinician Global Impression of Severity [CGIS], Clinician Global Impression of Change [CGIC]), and Meaningful Change Question (to be answered after each completion of the PGIC). An electronic PRO system will be used during the study to allow patients to complete the study questionnaires electronically.

The MACrO₂ PRO will be completed twice before the first dose of study drug to assess test-retest reliability (within 1 to 2 weeks prior to randomization, and on randomization day prior to study drug administration) and once weekly for the first 6 months of the study; other PROs and global assessment scales will be completed at baseline and once monthly for the first 6 months of the study. The QOL-B, NTM Symptoms Module, SGRQ-C, and PGIS will also be completed during Screening for test-retest reliability assessment. The PGIC, CGIC, and Meaningful Change Question will not be completed at baseline. After Month 6, all PROs will be completed every 3 months (84 days \pm 7 days), at End of Therapy (EOT), and at Late Follow Up (LFU). Sputum samples for microbiological assessments will be collected during the Screening period, once monthly for the first 6 months of the study, and then every 3 months (84 days \pm 7 days), at EOT, and at LFU.

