3.1.2 Definition of Baseline

For PRO data entered by the patient (MACrO₂, QOL-B, NTM Symptoms Module, SGRQ-C, or PGIS), baseline is defined as the last entry recorded by the patient on or prior to the first dose of study drug + 1 day (ePRO-specified close of window to further entry to patients).

For PRO data entered by the site (CGIS), baseline is defined as the last entry recorded by the patient on or prior to the first dose of study drug + 6 days (ePRO-specified close of window to further entry to sites).

For microbiological data, baseline pathogen(s) are determined based on MAC pathogens isolated from all MAC-positive respiratory samples collected within the 8-week Screening Period prior to the first dose of study drug, with specific representative baseline pathogen(s) confirmed by blinded Sponsor review.

For all other efficacy and safety endpoints, baseline is defined as the last measurement or assessment prior to first dose of study drug, including results from unscheduled visits if applicable.

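### The exploratory Phase 3 MMRM takes change from baseline as its response but counts Baseline as a response visit, so the unstructured fit is degenerate and the fallback standard errors are too small

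*SAP*

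**What the plan says.** The response in SAP Section 3.4.3.4 is "Change from baseline in continuous PROs, including QOL-B respiratory domain score", together with the MACrO₂ total scaled score, the NTM Symptoms domain and the SGRQ-C total. The model terms are treatment, "visit (from Baseline to Month 6 inclusive), and treatment by visit interaction as explanatory variables, and corresponding baseline score as a continuous covariate". On covariance: "The participant effect will be fitted as a random effect and an unstructured covariance structure will be assumed for within participant variation". If that fails to converge, "covariance matrices of Toeplitz, first-order autoregressive, and compound symmetry will be used in that order until the model converges". Tests use Kenward-Roger degrees of freedom. Least squares means, 95% intervals and p-values are reported at Months 3 and 6 in the Micro-ITT and PP populations, with a comparison of slopes from baseline to Month 6.

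Under Section 3.1.2, for patient-entered PROs "baseline is defined as the last entry recorded by the patient on or prior to the first dose of study drug + 1 day". Section 2.2.1 gives the schedule: "other PROs and global assessment scales will be completed at baseline and once monthly for the first 6 months of the study". The visit factor therefore has seven levels, Baseline and Months 1–6. Nothing elsewhere in the SAP limits this model's response to post-baseline visits.

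**The concern.** A Baseline level suits a model of raw scores. In a model of change scores it adds, for every patient in both arms, an observation fixed at zero by definition. This raises three problems.

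- The row has no variance of its own, so an unstructured matrix that includes it is singular.
- Each named fallback has one variance for all visits unless a heterogeneous form is stated, and none is. The zero row pulls that variance down, and with it the standard error at every later visit.
- A random participant effect on top of an unstructured within-participant matrix adds a parameter the matrix already contains.

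At stake are the p-values and intervals at Months 3 and 6 for four PROs. Two of them, the QOL-B respiratory domain and the MACrO₂ total scaled score, are also hierarchical endpoints under ANCOVA. The MMRM is the Phase 3 model of the continuous scores that uses all monthly visits, so it is a natural cross-check on an ANCOVA that leaves out most patients with no Month 6 score. Its error is in the anti-conservative direction.

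**Working it through.** **Inputs.** From the SAP: seven response levels, one common baseline slope, the covariance sequence, 2:1 allocation and two-sided 5% (Sections 2.2.7 and 3.4.3.4). Assumed, because the documents give neither SD nor correlation: equal raw-score SD at every visit (set to 1), and raw-score correlation that is exchangeable at 0.5–0.8, AR(1) at 0.90–0.95 per month, or a mix of the two.

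**The plan's own figure.** No standard error or power is stated for the MMRM. The only figure to reproduce is Phase 3 power, used here just to fix N. With 124 and 62 patients at 30% and 10%, the pooled rate is 0.2333. The null SE is √(0.2333 × 0.7667 × (1/62 + 1/124)) = 0.0658 and the alternative SE is √(0.09/62 + 0.21/124) = 0.0561. Power is Φ((0.20 − 1.96 × 0.0658)/0.0561) = 89.7%. Exact enumeration of the unstratified Miettinen-Nurminen test gives 90.7%. Both agree with the stated 90% or so at N = 186.

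**Unstructured fit.** At slope β the Baseline residual is −β times centred baseline, with variance proportional to β². So −2 log L contains 186 × ln(β²), which falls by 186 × 2 × ln 10 = 857 for each tenfold reduction in β. On simulated data:

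| β | −2 log L |
|---|---|
| −0.4 | 7724 |
| −0.01 | 6351 |
| −0.001 | 5495 |
| −1e-8 | 1212 |

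The step from −0.01 to −0.001 is 856, as predicted. The condition number of the matrix reaches 4e16. There is no maximum to converge to.

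**Fallbacks, one case by hand.** Take compound symmetry with exchangeable correlation 0.6. At slope β, each month has residual variance v = 1 − 1.2(1+β) + (1+β)², and the Baseline row has β². The fitted common variance is their average, so model SE / true SE = √[(6v + β²)/(7v)].

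- At the correct slope, β = −0.4: v = 0.64, and √[(3.84 + 0.16)/4.48] = 0.945.
- At β = 0: √(6/7) = 0.926.

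The zero row attenuates the slope, so the fit lies between these two. Without the row the ratio is 1.00.

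**Fallbacks, all cases.** Large-sample fits of Toeplitz, AR(1) and compound symmetry, giving model SE / true SE:

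| Assumed correlation | Visit | Row kept | Row removed |
|---|---|---|---|
| Exchangeable 0.5–0.8 | Months 3 and 6 | 0.912–0.944 | 1.000 |
| Decaying or mixed | Month 6 | 0.729–0.854 | 0.789–0.916 |
| Decaying or mixed | Month 3 | 0.908–0.985 | 0.979–1.057 |

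The Baseline row's own share is kept over removed: for example 0.729/0.789 = 0.924 and 0.854/0.916 = 0.932, or 0.912–0.944 under exchangeable correlation. That is about 6–9% throughout. The rest arises because the variance of a change score grows with time when correlation decays, and an equal-variance structure averages over that growth. Adding a random intercept to AR(1) changed the ratios by at most 0.001 in the decaying and mixed cases.

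**Test size.** By normal approximation, size = 2[1 − Φ(1.96 × ratio)]. Ratios of 0.944 and 0.912 give 6.4% and 7.4%; 0.854 and 0.729 give 9.4% and 15.3%. REML simulation at N = 186 with exchangeable correlation 0.6 and 500 replicates, at Month 6:

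| Structure | Dropout | Row kept: ratio, size | Row removed: ratio, size |
|---|---|---|---|
| AR(1) | none | 0.929, 7.4% | 1.009, 4.2% |
| Compound symmetry | none | 0.926, 8.0% | 1.006, 4.6% |
| AR(1) | 20% | 0.937, 7.0% | 1.016, 4.0% |

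The Monte Carlo standard error at about 7.5% is √(0.075 × 0.925/500) = 1.2 points. Toeplitz was covered by the large-sample fits but not simulated.

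**The case against.** The strongest reply is that the Baseline level is leftover wording. The SAP's version history records a switch of the PRO response to change from baseline, and the phrase may also be meant for the slope comparison. Programming specifications are in a separate document, and a programmer might well drop the row. That is possible, but the SAP as written includes it, and dropping it after the specified model fails would be an unplanned choice.

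The analysis is also exploratory. This stands: the US primary analysis is an ANCOVA at Month 6 with its own sensitivity analyses (Section 3.4.3.1), and alpha control covers only the hierarchical endpoints (Section 3.4).

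Three stronger readings are tempting and not supported.

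- A reader who simulates one setting might quote a single shortfall such as 11–13%. The documents fix neither correlation nor SD, and the figure moves with both visit and correlation pattern.
- A reader might call this the only analysis that uses all the monthly PRO data. Section 3.4.3.3 also has monthly descriptive summaries and monthly responder analyses, and Section 3.4.3.4 has time to sustained response.
- A reader might see the omission of ALIS use and fibrocavitary disease as adding to the anti-conservatism. Leaving out prognostic strata usually widens standard errors; it is an inconsistency with the ANCOVA, no more.

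**Conclusion.** The specification is wrong as written. Its first-choice covariance model is degenerate, and the fallbacks, read as equal-variance forms, understate the standard errors for all four continuous PROs. About 6–9% of the shortfall is due to the Baseline row under every correlation pattern tried. The total is about 2–27%: 6–9% at both visits under exchangeable correlation, and under decaying or mixed correlation 15–27% at Month 6 and 2–9% at Month 3. Part of the latter would remain after the row is removed. A nominal 5% test becomes roughly 7–8% under exchangeable correlation and, by normal approximation, about 9–15% at Month 6 under decaying or mixed correlation.

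These sizes rest on assumed correlations, equal raw-score SDs and the planned N. The trial stopped early, so Phase 3 may be smaller, but the ratios hardly depend on N. No confirmatory conclusion is affected: neither the ANCOVA nor the hierarchical tests use this model.

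**What to change.** In Section 3.4.3.4:

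- Define the response visits as Months 1–6, with baseline score as a covariate only.
- Drop the random participant effect when the within-participant matrix is unstructured.
- Name heterogeneous fallbacks: heterogeneous Toeplitz, ARH(1), then CSH. This deals with the part of the shortfall that removing the row leaves behind.
- Optionally, add ALIS use and fibrocavitary disease for consistency with the ANCOVA.

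The slope comparison does not need the zero row, because change at baseline is known to be zero. The cost is a few words of SAP text and a few lines of SAS, best made before Phase 3 unblinding. Under Section 1 a later change would have to be documented as a deviation in a post hoc addendum or the CSR.

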Results from the Phase 2 part of the study ongoing will inform the specific PRO and the clinical response definition selected to measure the primary endpoint, and the sample size re-estimations to be used, in the Phase 3 part of the study.

2.2.2 *Number of Patients*

A total of approximately 314 patients will be enrolled in this Phase 2/3 study:

- The Phase 2 part of the study will consist of approximately 80 patients randomized in a 1:1 ratio (40 patients in the epetraborole + OBR group and 40 patients in the placebo + OBR group). Randomization will be stratified by baseline use of ALIS and age at informed consent (<65 years versus \geq 65 years).
- The Phase 3 part of the study will consist of approximately 234 patients randomized in a 2:1 ratio (156 patients in the epetraborole + OBR group and 78 patients in the placebo + OBR group). Randomization will be stratified by baseline use of ALIS and the presence or absence of any fibrocavitary disease. The number of patients in the Phase 3 part of the study may be adjusted based on the results of Phase 2 analyses.

2.2.3 *Study Duration*

For the Phase 2 and Phase 3 parts of the study, the duration of study participation for each patient, not including Screening, will be up to approximately 19 months (see additional details in Protocol Section 3.1.1). Study participation for each patient includes the following:

- **Screening Visit:** Within 8 weeks prior to randomization.
- **Treatment Period:** Day 1 to EOT; the treatment period for each patient will vary, up to a maximum of 16 months, depending on the patient's sputum culture results; see details in Protocol Section 3.1.1.
- **EOT Visit:** Within 7 calendar days after the last dose of study drug.
- **LFU Visit:** 3 months (84 days \pm 14 days) after the last dose of study drug.

2.2.4 *Sites*

This Phase 2/3 study will be conducted globally at approximately 140 sites.

2.2.5 *Study Drug*

- Epetraborole oral tablets: 250 mg
- Epetraborole dosage: 500 mg (two 250-mg oral tablets) once daily (QD)
- Placebo oral tablets: Matched to epetraborole tablets

- Placebo regimen: Matched to epetraborole dosage [two oral tablets once daily (QD)]

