It was originally anticipated that the primary endpoint would be MACrO₂ PRO symptom-based clinical response at Month 6 for the Phase 3 part of the study (in the US). However, based on review of the overall Phase 2 analysis results along with ongoing advances in PRO literature and other public announcements in this therapeutic area prior to this version of the SAP, the change from baseline to Month 6 in QOL-B respiratory domain score has been chosen as the primary efficacy endpoint in the US in this updated analysis plan. Additionally, as part of the psychometric evaluation of the MACrO₂ PRO based on the blinded Phase 2 analysis results along with recommendations received from the FDA's Patient Focused Statistical Scientists (PFSS) reviewers, a new MACrO₂ total scaled score (Appendix 8.5) was introduced as an additional secondary efficacy endpoint in the Phase 3 analyses. By-patient sputum culture conversion by Month 6 has been retained as the key secondary endpoint in the US (and primary endpoint outside the US). Formal estimands are provided in the following sections for primary endpoints and key secondary endpoints in each phase, based on these revised endpoints. Due to the change in Phase 3 efficacy endpoints, a revised hierarchical testing order for Phase 3 in the US will be as follows: 1. QOL-B respiratory domain score change from baseline to Month 6 (primary efficacy endpoint in the US); 2. MACrO₂ total scaled score change from baseline to Month 6; 3. By-patient sputum culture conversion by Month 6. The revised hierarchical testing order for Phase 3 outside the US will be as follows: 1. By-patient sputum culture conversion by Month 6 (primary efficacy endpoint outside the US); 2. QOL-B respiratory domain score change from baseline to Month 6; MACrO₂ total scaled score change from baseline to Month 6.

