QOL-B respiratory domain scores are measured on a scale from 0 to 100 (with higher scores indicating better health-related quality of life). QOL-B respiratory domain scores will be summarized by visit in the Micro-ITT Population. Descriptive statistics of both the reported QOL-B respiratory domain scores and change from baseline will be reported by visit (monthly through Month 6). Change from baseline to Month 6 in QOL-B respiratory domain score will be analyzed using an analysis of covariance (ANCOVA) model, including baseline score, treatment and either including (primary analysis) or excluding (sensitivity analysis 1) stratification factors of baseline ALIS use and the presence or absence of any fibrocavitary disease as covariates. Least squares means, 95% confidence intervals, and p-values of the treatment comparison will be presented for both the Micro-ITT (primary) and PP (sensitivity) populations.

Patients who fail to provide a complete QOL-B respiratory domain score at both baseline and Month 6 will be excluded from the analysis and considered unbiased under the missing at random (MAR) assumption, with the exception of patients experiencing intercurrent events, which will be accounted for following the imputation rules above. However, in an additional pair of sensitivity analyses, the primary efficacy analysis will be repeated as described above, but applying a treatment policy strategy in which results for patients with new, additional non-study-specific, antimycobacterial therapy that is potentially effective against MAC, or surgery for MAC lung disease, for reasons other than clinical failure of study drug, will be used as recorded. These models will be run using the ANCOVA model as described above, including baseline score, treatment and either including (sensitivity analysis 2) or excluding (sensitivity analysis 3) stratification factors of baseline ALIS use and the presence or absence of any fibrocavitary disease as covariates.

3.4.3.2 Phase 3 Primary Efficacy Endpoint Outside the US (Key Secondary Endpoint in the US)

The primary efficacy outside the US (secondary in the US) is by-patient sputum culture conversion monthly through Month 6. The Estimand corresponding to the primary endpoint is defined with the following five attributes:

1. Population: Patients with MAC culture-positive Pre-Study and Screening respiratory specimens

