Descriptive statistics of both the reported scores and change from baseline (for continuous scores only) will be reported by visit (monthly through Month 6) for scores for all PROs collected in the study (QOL-B domain scores, MACrO₂ total scaled score, NTM Symptoms Module, SGRQ-C, PGIS, PGIC, CGIS, CGIC, and Meaningful Change Question) based on the Micro-ITT Populations. Change from baseline score at Month 3 and Month 6 of selected continuous PROs including QOL-B respiratory domain score (Month 3 only, as Month 6 is the primary efficacy analysis), MACrO₂ total scaled score, NTM Symptoms Module domain score, and SGRQ-C total score will be analyzed using an analysis of covariance (ANCOVA) model, including baseline score, treatment and stratification factors (baseline ALIS use and presence or absence of any fibrocavitary disease) as covariates. Least squares means, 95% confidence intervals, and p-values of the treatment comparison will be presented for both Micro-ITT and PP populations. Intercurrent events will be handled following the same rules as for the primary efficacy analysis.

Clinical response as defined above for the MACrO₂ PRO as well as for each additional PRO measure according to pre-defined response thresholds relative to baseline will be examined monthly through Month 6. MACrO₂ original responder is defined as improvement of ≥ 1 grade in the key symptom with no worsening of other symptoms. Response in QOL-B respiratory domain score is defined as an improvement

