Clinical response as defined above for each individual PRO endpoint point (QOL-B respiratory domain, MACrO₂ original responder definition and response in total scaled score by threshold, SGRQ-C, NTM Symptoms Module, PGIS, CGIS, PGIC, and CGIC) will be presented dichotomously (Yes/No) for each treatment arm and will be presented as the treatment difference and associated 95% confidence interval and p-value, calculated using the method of Miettinen and Nurminen stratified by baseline use of ALIS and the presence or absence of any fibrocavitary disease for both the Micro-ITT and PP populations. In addition, to examine the influence of baseline severity on the treatment effect, clinical response rate by month will also be analyzed using a logistic regression model, including treatment and baseline key symptom severity (for MACrO₂ original responder definition only), baseline score (for QOL-B respiratory domain, MACrO₂ total scaled score, SGRQ-C Total Score, NTM Symptoms Domain), baseline severity in CGIS (for CGIS and CGIC), or baseline severity in PGIS (for PGIS and PGIC) as covariates. Stratification factors of baseline ALIS use and the presence or absence of any fibrocavitary disease will also be included as covariates in each model. For each logistic regression model, the estimated odds ratio and 95% confidence interval and corresponding p-value for the treatment effect will be presented.

Line plots of mean score (\pm SD) as well as mean (\pm SD) change from baseline in score over time will be produced for continuous PROs (e.g., QOL-B domain scores, MACrO₂ total scaled score, NTM symptom module score and total SGRQ-C score), with the two treatment groups indicated with different colors on the plot. A bar plot of categorical PROs (e.g., proportion of MACrO₂ responders, PGIS, PGIC, CGIS, CGIC and Meaningful Change Question) by treatment group will also be produced by visit.

In order to assess the concordance of PRO changes with microbiological changes the following summaries will be produced for each PRO. These will be produced at Month 3 and 6, as specifically noted below:

- Summary of PRO response (Response/Failure) versus sputum culture conversion (Conversion/No Conversion) by Month 6
- Summary of PRO response (Response/Failure) at Month 3 versus sputum culture conversion (Conversion/No Conversion) by Month 6

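### The exploratory Phase 3 MMRM leaves out both randomization strata, and the Phase 3 Cox models have no usable covariate list

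*SAP*

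**What the plan says.** SAP 2.2.2 sets the Phase 3 design: "Randomization will be stratified by baseline use of ALIS and the presence or absence of any fibrocavitary disease".

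The Phase 3 analyses then use those factors as follows.

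- **US primary endpoint (SAP 3.4.3.1).** The Month 6 change in QOL-B respiratory domain score is analyzed by ANCOVA, "including baseline score, treatment and either including (primary analysis) or excluding (sensitivity analysis 1) stratification factors of baseline ALIS use" and fibrocavitary disease. The model without strata is thus a labelled sensitivity analysis.
- **Secondary continuous scores (SAP 3.4.3.3),** including the MACrO₂ total scaled score: ANCOVA "including baseline score, treatment and stratification factors (baseline ALIS use and presence or absence of any fibrocavitary disease) as covariates".
- **PRO responder logistic models (SAP 3.4.3.3):** "Stratification factors of baseline ALIS use and the presence or absence of any fibrocavitary disease will also be included as covariates in each model".
- **Miettinen-Nurminen comparisons** of culture conversion (3.4.3.2), microbiological improvement and PRO response (3.4.3.3) and radiographic response (3.4.3.4) are stratified by both factors. Where an unstratified version is planned, it is called a sensitivity analysis.
- **MMRM (SAP 3.4.3.4):** randomized treatment, visit and "treatment by visit interaction as explanatory variables, and corresponding baseline score as a continuous covariate". No strata appear and no reason is given. The model reports least squares means, 95% intervals and p-values at Months 3 and 6 in the Micro-ITT and PP populations.
- **Cox models (SAP 3.4.3.4),** for three times to sustained PRO improvement: "Time to event will also be analyzed using a Cox proportional hazard model with the same variables as the previous exploratory analysis".

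**The concern.** When randomization is balanced within prognostic strata and a linear model ignores them, the estimate is more precise than the model reports. The model leaves the stratum variance in its residual, although stratified allocation has already removed most of that variance from the treatment contrast. The interval is then too wide and the test too cautious.

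The MMRM is the model that uses the continuous scores jointly across visits, so it will naturally be read beside the Month 6 ANCOVA. With different covariates, a difference between the two could come from the repeated-measures handling or from the adjustment.

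The Cox problem is one of specification. Two programmers could fit different covariate sets and each could claim to have followed the plan.

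**Working it through.** **Covariates side by side.** Among the Phase 3 models and tests whose covariates or strata are listed, the MMRM is the only one without both stratification factors that is not labelled a sensitivity analysis.

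**Sample size used.** The plan has no precision figure for the MMRM. The only design figure is the responder calculation in SAP 2.2.7: 124 + 62 = 186 Micro-ITT patients, 30% versus 10%, two-sided alpha 0.05, about 90% power. With pooled p = (37.2 + 6.2)/186 = 0.2333:

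- null SE = √[0.2333 × 0.7667 × (1/124 + 1/62)] = 0.0658
- alternative SE = √(0.21/124 + 0.09/62) = 0.0561
- power = Φ[(0.20 − 1.96 × 0.0658)/0.0561] = Φ(1.27) = 89.7%

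Exact enumeration of the unstratified score test gives 90.7%. The stated figure reproduces, and 186 is used below.

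**MMRM interval width.** Let R² be the share of residual variance, given baseline score, that the two strata explain. Ignoring degrees of freedom, width without strata ÷ width with strata ≈ √[1/(1 − R²)].

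The check was a simulation with a single-visit ANCOVA standing in for the MMRM: 186 patients, 2:1 stratified blocks of six, 30% ALIS use, 40% fibrocavitary disease, no treatment effect, 4,000 runs per row. R², the two prevalences and the block size are assumptions.

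| R² | Formula | Width with strata | Width without | Ratio | Coverage with | Coverage without |
|---|---|---|---|---|---|---|
| 0 | 1.000 | 0.615 | 0.615 | 1.000 | 95.3% | 95.2% |
| 0.02 | 1.010 | 0.609 | 0.615 | 1.010 | 95.2% | 95.5% |
| 0.05 | 1.026 | 0.599 | 0.614 | 1.026 | 94.7% | 95.3% |
| 0.10 | 1.054 | 0.583 | 0.615 | 1.054 | 94.8% | 96.1% |
| 0.20 | 1.118 | 0.549 | 0.615 | 1.118 | 94.8% | 96.8% |

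The excess width is 2.6%, 5.4% and 11.8% at R² of 0.05, 0.10 and 0.20. Coverage without strata is at or above 95%, so the error is conservative.

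A second simulation (four equal strata, blocks of three, 6,000 runs) put this in terms of power. Adding the strata raised power from 79.9% to 81.3%, from 80.2% to 83.3% and from 82.1% to 87.6% at the same three values, which are gains of 1.4, 3.1 and 5.5 points.

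**What the Cox reference points to.** The only regression model earlier in 3.4.3.4 is the MMRM. Its visit and treatment-by-visit terms index repeated scores and have no role in a model for one event time per patient. The section's opening exploratory analysis is a descriptive subgroup display whose list includes ALIS use and fibrocavitary disease, along with age, sex, country and others. It is not a model either. The SAP version history records that Phase 3 exploratory logistic models were removed. They may be what the phrase once pointed to, but that is context only.

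**Effect of omitting strata from a Cox model.** Simulation with 186 patients, true hazard ratio 1.8, follow-up to Day 169, the same prevalences and blocks, and 500 runs per row:

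| Log hazard coefficient of each stratum (absolute) | Log HR with strata | Log HR without | Reduction | SE without ÷ with |
|---|---|---|---|---|
| 0 | 0.607 | 0.603 | 0.6% | 0.998 |
| 0.3 | 0.614 | 0.605 | 1.5% | 0.999 |
| 0.6 | 0.596 | 0.573 | 3.8% | 0.998 |
| 1.0 | 0.612 | 0.565 | 7.7% | 0.998 |

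The standard error does not grow. The estimate shrinks: in the last row the hazard ratio is exp(0.565) = 1.76 instead of exp(0.612) = 1.84.

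**The case against.** The case against is strong on consequence. The MMRM is headed exploratory. It lies outside the hierarchy in SAP 3.4 and is not among the numbered sensitivity analyses in 3.4.3.1. For the US primary endpoint, sensitivity analysis 1 is an ANCOVA without strata, so an analysis with the same baseline covariates as the MMRM already exists. The size rests on an R² that the documents do not supply, and the error is conservative. All of this stands, and it limits the point to a minor one. It does not explain why the MMRM alone drops the strata without a label. Nor does the plan state an unstratified ANCOVA for the secondary scores to set beside the MMRM.

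Four stronger readings are tempting, and the documents do not support them.

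- **That intervals for the main PRO endpoints are too wide.** Those for the QOL-B respiratory domain and the MACrO₂ total scaled score come from stratum-adjusted ANCOVAs. SAP 3.1.4 does call for a longitudinal analysis of domain and total scores, but the endpoint sections name ANCOVA. That wording should be reconciled separately.
- **That only the MMRM uses scores before Month 6.** The Month 3 ANCOVA and the monthly logistic models do too, with strata.
- **That the Cox models are specified without strata, and so have inflated intervals.** The reference is unresolved, not demonstrably free of strata, and omission acts on the estimate.
- **That leaving out the strata undermines the missing-at-random assumption.** Nothing in the documents links either factor to dropout, and SAP 3.1.4 says that missing data are not expected.

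**Conclusion.** The point holds as a small improvement to exploratory analyses. Relative to a stratum-adjusted fit, the MMRM intervals would be wider by about 3%, 5% and 12% at R² of 0.05, 0.10 and 0.20, and not at all if the strata are not prognostic. There is no added false-positive risk, and no primary or hierarchically tested result changes.

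The Cox covariate list cannot be determined from the text, and that conclusion needs no assumption about effect size. If prognostic strata were left out, the log hazard ratio would be attenuated by about 1% to 8% over the range simulated.

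The figures rest on the assumed R², stratum prevalences and stratum effects, on a single-visit stand-in for the MMRM, and on the planned 186 patients. SAP Section 1 reports early termination, so the actual Phase 3 number may be smaller.

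**What to change.** In SAP 3.4.3.4:

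1. Add baseline ALIS use and presence or absence of fibrocavitary disease to the MMRM as fixed effects.
2. Replace the Cox back-reference with an explicit list: treatment, the corresponding baseline score (or baseline key-symptom severity for the MACrO₂ responder definition), and both stratification factors as covariates, as in the SAP's logistic models.

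The cost is two sentences, two model degrees of freedom in the MMRM and a small code change, with no new data. The change is best made before Phase 3 is unblinded. After that, SAP Section 1 requires it to be documented in a post hoc addendum, the study report or both.
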